Method and materials: 180 gender-balanced groups were divided into four groups: MIX, DNS, VIBRO, and CONTROL, and underwent two months of treatment. The single and double-leg Center of Force (COF) parameters were collected on the Forceplate.

Detailed Description

Study design

The purpose of this study is to determine the effects of dynamic neuromuscular stabilisation (DNS), whole-body vibration (WBV), and a combination of DNS and WBV (MIX) training modalities on postural stability (PS) in healthy recreation participants. The study presents an Interventional study to improve postural stability, and the main objective is prevention. The study model is parallel with four groups.

Participants

The randomised, controlled interventional trial enrolled a gender-balanced group of 180 healthy young participants. The initial sample of respondents was recruited through an open online application that lasted two months (from 10.2.2022. to 10.4.2022.) (n=250), after which the first selection of respondents was started (n=230). Recruitment was completed after the optimal sample of subjects was filled (15.4.2022). The study sample was divided using stratified randomisation into the MIX group (n = 58), DNS group (n=57), VIBRO (n=57), and CONTROL group (n=58). At the end of the experimental program, the final sample was 180 (MIX=45; DNS=45; VIBRO=44; CONTROL=43). When stratifying, researchers use proportionate sampling to maintain the correct proportions of genders in every group. After explaining the experimental protocol, each subject provided written informed consent before participating in the study, per the Declaration of Helsinki and the Novi Sad University Human Research Ethics Committee guidelines (ethical approval number: 46-06-04/2020-1). The interventional program was conducted from 25.4.2022. to 25.6.2022.

[figure not shown]
Ethics committee – commission for implementation of scientific project research

The exclusion criteria were:

- history of neurological or musculoskeletal disorders;
- clinical conditions that could impair balance (motor disorders, medical conditions like diabetes, heart disease, stroke, issues with vision, thyroid, nerves, or blood vessels).

The inclusion criteria for this study were:

- the absence of injuries in the past six months
- the absence of other medical conditions, including COVID-19
- no programmed physical activity in the past three months.

Testing procedures

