Tests for static PS were the gold standard in measuring balance and were used to obtain biomechanical parameters of static PS (Hass et al., 2008). All measurements were performed in triplicate, and the mean score was retained for subsequent evaluations and analyses. The sequence of performing the balance tasks was randomised.

The software calculated the single and double-leg Sway Area (cm^2), Center of Force (COF) travelled way (mm), Medio-Lateral (ML) displacement (mm), and Anterior-Posterior (AP) displacement (mm) as primary outcomes. The following protocol was chosen based on their varying difficulty and common use as stated in previous research and is cited as reliable (Bauer et al., 2008; Springer et al., 2007; Troester et al., 2018; Verhagen et al., 2005).

Interventions

Dynamic neuromuscular stabilisation group (DNS)

DNS group's protocol involved 5 min a moderate intensity warm-up, 40 minutes of DNS movements according to the DNS approach(Frank et al., 2013), different diaphragmatic breathing, mobility and controlled movement exercises and 5 minutes of cool-down. Exercises gradually increased in complexity and difficulty level regarding DNS training principles (Mahdieh et al., 2020). The participants were instructed to refrain from engaging

in high-intensity anaerobic or anaerobic resistance training throughout the study period to prevent potential disruptions in the study results.

Whole body vibration group (VIBRO)

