G*power 3.1 power analysis software (Heinrich-Heine-University, Düsseldorf, Germany) estimated the minimum total sample size ($N=140$) given the critical $F_{(3, 136)}=2.67$, an effect size $f=0.14$ (partial $\eta^2=0.02$), $p=0.05$, $1-\beta=0.80$, groups=4, time points=2, and correlation among the measurements=0.50. The authors presented data as means and 95% confidence intervals [95% CIs]. The Kolmogorov-Smirnov, Leven's, Box's, and Mauchly's tests confirmed the assumptions of normality, homogeneity of variances and covariances, and sphericity, respectively. General linear models (twelve separate 2x4 mixed-design analyses of covariances for each PS measure) estimated whether mean changes [95% CIs] in PS measure from initial to final testing depended on whether participants received the DNS, VIBRO, and MIX exercise program or did not (CONTROL) after controlling for mean-centered BMI (Cibulková et al., 2022; Hue et al., 2007). Following the time-by-group interaction effects, which revealed whether estimated changes over time depended on the participants' group (i.e., differed at least between one group-comparison pair), we computed simple effects tests to estimate mean changes over time (mean difference from initial to final testing) within the groups. The follow-up investigation proceeded with contrast analysis, which assessed the degree to which estimated mean changes of PS measures differed between the group-comparison pairs. The authors calculated the effect size for time-by-group interaction effects and simple effects using partial eta squared (partial η^2 : 0.01 small; 0.06 medium; 0.14 large) (Cohen, 2013) and Hedge's g average (Hedge's s_{av} : $<|0.20|$ trivial; $|0.20|$ small; $|0.50|$ medium; $|0.80|$ large) (Lakens, 2013), respectively. The Bonferroni test corrected p-values and 95% CI; the alpha level was $p\leq0.05$. We used SPSS version 23.0 (SPSS Inc., Chicago, IL, USA) and GraphPad Prism version 8.0 (GraphPad Software, San Diego, California, USA) to analyse and plot the data, respectively.

References

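### The planned model compares change scores adjusted only for BMI; adding each measure's initial value would cut contrast standard errors by about 13% at the protocol's own correlation.

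*Protocol*

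**What the plan says.** The Statistical analyses section describes twelve separate 2x4 mixed-design analyses of covariance, one per measure. Each one "estimated whether mean changes [95% CIs] in PS measure from initial to final testing depended on whether participants received" one of the three programmes or "did not (CONTROL) after controlling for mean-centered BMI". After the time-by-group interaction come simple effects within groups, and then contrasts, "which assessed the degree to which estimated mean changes of PS measures differed between the group-comparison pairs". On multiplicity it says: "The Bonferroni test corrected p-values and 95% CI". No covariate other than BMI is named. The initial value enters only as one of the two repeated outcomes.

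The sample-size statement in the same section gives N=140 for four groups, two time points, f=0.14 (partial eta squared 0.02), alpha 0.05, power 0.80, "and correlation among the measurements=0.50".

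**The concern.** With two time points, the time-by-group interaction and its contrasts are algebraically a comparison of final-minus-initial differences between groups. Differencing already removes a stable effect of BMI on the level of sway, so BMI sharpens these tests only as far as it predicts change. The initial value of the same measure usually predicts change better. A participant who happens to score high at the start tends to move back towards the mean, and the change score carries that movement as noise.

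The aim is to compare DNS, WBV, their combination and no training, so the pairwise contrasts are the comparative result, and they carry a Bonferroni penalty as well. Leaving out the initial value makes their intervals wider than the data require. Chance baseline imbalance is part of this same variance and is not a separate harm.

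**Working it through.** **Inputs from the protocol.** Correlation rho=0.50, f=0.14 or partial eta squared 0.02, alpha 0.05, power 0.80, four groups, two time points, N=140 (Statistical analyses); final arms 45, 45, 44 and 43 (Participants). **Assumptions.** Ratio k of final to initial SD (the protocol gives no SDs), six pairs in the Bonferroni family, and correlations other than 0.50.

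**1. The plan's own figure.** For the interaction, lambda = 2N f²/(1−rho), with 3 and N−4 degrees of freedom. The critical F(3,136) is 2.67, as stated. Partial eta squared 0.02 gives f = sqrt(0.02/0.98) = 0.143. The smallest multiple of four reaching 0.80 is then N=140 (power 0.808), so the stated N is reproduced. With f rounded to 0.14, power at 140 is 0.790 and N would be 144.

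**2. Precision with and without the initial value.** With initial SD s:

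- Variance of change: s²(1 + k² − 2 rho k)
- Residual variance given the initial value: s² k²(1 − rho²)
- Ratio of the second to the first: k²(1 − rho²)/(1 + k² − 2 rho k), which is (1 + rho)/2 at k=1

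At rho=0.50 and k=1 the ratio is 0.75. The SE ratio is sqrt(0.75) = 0.866, a cut of 13.4%. The equivalent increase in N is 1/0.75 = 1.33. A simulation of the BMI-adjusted models at 45/45/44/43, with BMI unrelated to the outcome, gave mean SEs of 0.213 and 0.185 SD, a cut of 13.0%.

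**3. Sensitivity.** Percentage cut in SE:

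| k | rho 0.30 | rho 0.50 | rho 0.70 | rho 0.80 |
|---|---|---|---|---|
| 0.8 | 29 | 24 | 21 | 20 |
| 1 | 19 | 13 | 8 | 5 |
| 1.25 | 11 | 5.5 | 1 | 0 |

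The gain vanishes at k = 1/rho. Both models include BMI, so strictly rho is the correlation given BMI. If 0.50 is the raw value and BMI correlates 0.3 with sway at both tests (assumed), the partial correlation is (0.50 − 0.09)/(1 − 0.09) = 0.45 and the cut is 15%.

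**4. Pairwise interval, 45 versus 43, k=1, rho=0.50.** sqrt(1/45 + 1/43) = 0.2133. The critical t at two-sided 0.05/6 is 2.669, with 172 degrees of freedom as planned and 171 adjusted.

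- Planned: SE = 0.2133 × sqrt(2 × 0.5) = 0.213; half-width 0.569 SD
- Adjusted: SE = 0.2133 × sqrt(0.75) = 0.185; half-width 0.493 SD

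As an illustration, if the true difference were 0.5 SD (assumed), power for this pair would go from 0.38 to 0.52 at rho=0.50, and from 0.85 to 0.89 at rho=0.80. If f=0.14 holds at rho=0.50, the SD of the arm mean changes is 2 × 0.14 = 0.28 SD. The largest pairwise difference is then between 0.56 and 0.79 SD, depending on the pattern of means. Power for that pair goes from about 0.48 to 0.64 at the lower end and from about 0.85 to 0.95 at the upper end.

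**5. Omnibus test at rho=0.50, k=1.** Adjustment multiplies lambda by 2/(1+rho) and uses N−5 degrees of freedom. For 0.80 power, N falls from 140 to 108 (f=0.143) or from 144 to 112 (f=0.14). At N=177, the sum of the final arms, power goes from 0.89 to 0.96 (f=0.14) or from 0.90 to 0.97 (f=0.143).

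**The case against.** The strongest reply is that nothing here is wrong. The planned test is unbiased under randomisation and matches the power calculation. With 177 analysed, its omnibus power at the assumed effect is already 0.89 to 0.90, above the 0.80 target. Recruitment closed in 2022, so a saving in sample size is of no use now. All of this stands, and it is why the point concerns precision only. It does not answer the case for narrower pairwise intervals, because the 0.80 target applies to the omnibus test and no target is stated for the pairs.

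The second reply is that 13% is one cell of a wide table. That is also fair: rho=0.50 is a planning value, and the twelve measures will each have their own correlation and SD ratio. The Testing procedures section says "All measurements were performed in triplicate, and the mean score was retained for subsequent evaluations and analyses"; averaging tends to raise the correlation, so a gain below 13% is plausible. The six-pair family and the 0.5 SD difference are illustrations, not protocol values.

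The third reply is timing. The document is dated February 19, 2024, final testing took place on 25.6.2022, and the Statistical analyses section reports that the named "tests confirmed the assumptions of normality, homogeneity of variances and covariances, and sphericity, respectively". The data appear to have been examined. This limits the form of the remedy, but it does not alter the comparison of the two models.

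**Conclusion.** The concern holds. The protocol fixes a change-score comparison with BMI as the only covariate and leaves the most obvious prognostic variable, already measured, out of the covariates. At the protocol's correlation and with equal variances the cost is a standard error about 15% larger than needed (1/0.866 = 1.155); put the other way, adjustment would cut it by 13.4%. Across the correlations and SD ratios examined the cut is 0% to 29%. The algebra is certain, but the realised gain for each measure is not known from the document. Neither bias nor inadequate power is claimed: pairwise power depends on the true differences and correlations.

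**What to change.** For each measure, fit the final value on group with the initial value of that measure and mean-centred BMI as covariates. Take the group contrasts and Bonferroni intervals from that model. Within-group changes can still be reported as description.

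If group results have already been seen, do not replace the planned model. Keep the 2x4 analysis as primary and report the baseline-adjusted model beside it for all twelve measures, labelled as a post hoc sensitivity analysis.

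The cost is small: one degree of freedom, no new data, and a model that SPSS already fits. Before an analysed N is quoted, reconcile the Participants section, which states 180 although its arms give 45 + 45 + 44 + 43 = 177.

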The testing was conducted at the Faculty of Sport and Physical Education, University of Novi Sad, Serbia. All participants were tested in the morning before their training session in indoor environmental conditions (temperature: 18–21°C; relative humidity: 40–60%). Before starting a performance task, general information about the examinees was recorded, including gender, age, height, and mass. Participants were instructed to wear minimal clothing and remove all footwear for height and mass measurements. In addition, they were required to eat and drink sparingly and void their bladder/excrete as needed before presenting for assessment. A stadiometer (0.1 cm accuracy, SECA Instruments Ltd, Hamburg, Germany) is used for height and mass measurements as a secondary outcome. Initial testing was conducted on 20.4.2022 and final on 25.6.2022.

Static PS was assessed with a laboratory-grade 0.5 m Footscan® plate (RSscan International, Lammerdries, Belgium) with 4096 sensors and a scanning rate of up to 300 Hz. The subject performed an individual single and double-leg task with three trials, each lasting 30 seconds with a two-minute break between each trial. During the double-leg stance test, participants were instructed to maintain an upright and as still as possible posture. They were asked to stand in their natural, comfortable position with their eyes open and fixed on a cross positioned at approximately eye level on a blackboard situated 5 meters away. Participants stood barefoot with their feet placed shoulder-width apart on a platform, and their arms were kept by their sides. Each participant was required to maintain this stable posture, and measurement started after 10 seconds (preparation period to avoid transient effects). During the single-limb stance test, participants were instructed to balance on one foot. This foot was positioned to point directly forward, aligning with reference lines in the frontal and sagittal planes. The swinging leg was flexed at the hip and knee joints to approximately 90 degrees while both arms hung naturally and relaxed at their sides. Participants were further instructed to maintain as steady a posture as possible, focusing their gaze straight ahead on a point situated 65 centimetres away on the wall. The order of testing between the left and right legs was randomised. Each participant was required to maintain this stable position, and measurement started after 5 seconds (preparation period to avoid transient effects).

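### Allocation is stratified by gender but all twelve models adjust for BMI alone, so the tests of change are slightly conservative if gender predicts change

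*Protocol*

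**What the plan says.** Protocol, Participants: 230 people were allocated by stratified randomisation to MIX, DNS, VIBRO and CONTROL (58, 57, 57 and 58). On the stratification the section says: "When stratifying, researchers use proportionate sampling to maintain the correct proportions of genders in every group". No other factor is named. The arms at the end are 45, 45, 44 and 43, which sum to 177.

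Protocol, Testing procedures: gender was collected from everyone, since "general information about the examinees was recorded, including gender, age, height, and mass".

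Protocol, Statistical analyses: each of twelve postural stability measures gets its own mixed-design analysis of covariance with time (2) and group (4). The groups are compared with those who "did not (CONTROL) after controlling for mean-centered BMI". The follow-up contrasts "assessed the degree to which estimated mean changes of PS measures differed between the group-comparison pairs". Gender does not appear in this section, and no reason is given for leaving it out. Two sources are cited in support of BMI.

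**The concern.** A factor used to constrain the allocation normally goes into the analysis as well. Stratification makes the arms alike in gender, so gender contributes little to the differences between arms. A model without gender does not know this. It estimates the error as if gender could vary freely between arms, so the standard error is larger than the true sampling variation of the contrast.

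The time-by-group test with two time points is a test on change. A constant gender difference in the level of sway therefore cancels out, and only a gender difference in the change from initial to final testing matters. If there is one beyond what BMI carries, the intervals for between-group differences are wider than the design earns and the tests reject too rarely under the null. At stake is a little precision in all twelve models.

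This is not a detail left to a statistical analysis plan. The Protocol itself fixes the model, the covariate, the follow-up tests and the software.

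**Working it through.** **Inputs from the Protocol.** Statistical analyses: f = 0.14 (partial eta squared 0.02), alpha 0.05, power 0.80, 4 groups, 2 time points, correlation 0.50, N = 140, critical F(3, 136) = 2.67. Participants: final arms 45 + 45 + 44 + 43 = 177.

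**Assumed.** R² is gender's share of the variance of change beyond BMI. It is not given, so 0, 2%, 5% and 10% are used. Gender is taken as balanced within each arm.

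**1. The plan's own figure.** For the within-between interaction, λ = f² × N × 2/(1 − 0.5), with 3 and N − 4 degrees of freedom.
- f = 0.14, N = 140: λ = 0.0196 × 140 × 4 = 10.976, critical F = 2.671, power 0.790.
- f = √(0.02/0.98) = 0.1429: λ = 11.429, power 0.808.

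The stated N = 140 reproduces with the unrounded effect size.

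**2. Standard errors.** Without gender the error variance is taken as 1; with gender it is 1 − R². The ratio of standard errors (without/with) is 1/√(1 − R²).

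**3. Type I error of the BMI-only test.** With gender balanced, the numerator of F carries variance 1 − R² and the denominator about 1. The rejection rate under the null is therefore approximately P(F(3, 172) > 2.657/(1 − R²)), where 172 = 177 − 5.

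**4. Power at N = 177, f = 0.14.** λ = 0.0196 × 177 × 4 = 13.877. In both models the noncentrality is λ/(1 − R²).
- With gender: P(F′(3, 171) > 2.657), with 171 = 177 − 6.
- BMI only: P(F′(3, 172) > 2.657/(1 − R²)).

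| R² | SE ratio | Type I, BMI only | Power, BMI only | Power, with gender |
|---|---|---|---|---|
| 0 | 1.000 | 0.050 | 0.886 | 0.886 |
| 2% | 1.010 | 0.047 | 0.887 | 0.892 |
| 5% | 1.026 | 0.042 | 0.888 | 0.902 |
| 10% | 1.054 | 0.034 | 0.891 | 0.918 |

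The BMI-only power values are approximate. A separate recomputation gave 0.888, 0.890 and 0.892 at 2%, 5% and 10%. Either way the gain from adding gender is about 0.4 to 0.6, 1.2 to 1.4 and 2.6 to 2.7 points. BMI-only power must not be held at 0.886 for every share, because balance also takes gender noise out of the numerator; doing so overstates the gain.

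**5. If balance holds at allocation only.** A simulation with balance at 58/57/57/58 and random loss to 45/45/44/43 (20,000 runs per setting, Monte Carlo error about 0.0015) gave BMI-only type I error of 0.048, 0.042 and 0.037, and 0.049 to 0.052 with gender in the model. The pattern is the same and slightly weaker.

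**The case against.** The strongest reply is that nothing here is wrong as such. The model is stated clearly and BMI is supported by citations. Nothing in the Protocol says that gender predicts change, and omitting a balanced factor errs on the safe side. At N = 177 the BMI-only test already exceeds its 80% target. At shares of 2% to 5% the standard errors are only 1.0% to 2.6% too large, which would hardly change a conclusion. The added term would also be chosen after the data were in.

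Most of this stands, and it limits the size of the point. The size rests wholly on assumed shares, BMI may carry part of any gender effect, and the direction is conservative. It does not remove the point: the analysis ignores the one factor used in the allocation, gives no reason, and could include it at almost no cost.

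A reader might go further and infer that loss after allocation upset the gender balance, so that the BMI-only contrasts are biased. The Protocol does not support this. Loss is similar across arms: 13/58 = 22%, 12/57 = 21%, 13/57 = 23% and 15/58 = 26%. The trial is described as having "enrolled a gender-balanced group of 180 healthy young participants". Gender counts by arm are not given, so differential loss is neither shown nor excluded. A large imbalance would need opposite patterns. Assuming 29 of each gender in MIX and in CONTROL at allocation, a gap of about 20 points (27/45 against 17/43) needs losses of 2 and 11 in MIX and of 12 and 3 in CONTROL.

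**Conclusion.** The point holds as a minor loss of efficiency. If gender explains 2%, 5% or 10% of the variance of change beyond BMI and is balanced within arm, the BMI-only tests run at about 0.047, 0.042 and 0.034 instead of 0.05. Standard errors are then about 1.0%, 2.6% and 5.4% too large, and up to about 2.7 points of power are given away. If gender does not predict change, nothing is lost.

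Two stronger readings should not be drawn. Type I error is not inflated; under balance the effect runs the other way. Bias from gender-related loss is not a consequence the document supports. The sample size of 140 is unaffected.

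**What to change.** Add gender and gender-by-time beside mean-centred BMI in all twelve models. Enter gender without a group-by-gender interaction, so that it costs a single degree of freedom in the test of change (171 instead of 172 at N = 177). No new data are needed.

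The term must be labelled as added after data collection: "The interventional program was conducted from 25.4.2022. to 25.6.2022", and the Protocol is dated February 2024. Show the BMI-only result beside the gender-adjusted one for each measure, so that readers can see whether the choice matters. The cost is that label and a second set of twelve results.

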Effect of different neuromuscular training modalities on postural stability in healthy recreation people: A randomised controlled trial

February 19, 2024

Title: Effect of different neuromuscular training modalities on postural stability in healthy recreation people: A randomised controlled trial

Brief Title: "Neuromuscular Training & Postural Stability"

Acronym: STABLEFIT

Study Overview

Brief Summary

Background: Postural stability (PS) is a vital function that helps maintain equilibrium during standing still, locomotion, and any activities requiring high balance performance. Under static and dynamic conditions, PS is a fundamental factor for the quality of movement in everyday activities or sports. PS and adaptive ability are required in sports due to the interactions between the sensory and motor systems, which regulate postural adjustments by processing information from the visual, vestibular, and somatosensory systems, as reported by previous studies. The interest in using different exercises and protocols for improving PS in sports and physiotherapy has grown in the last few decades. Experts have proposed various training modalities to increase neuromuscular stability, balance, postural control, and general stability.

Dynamic Neuromuscular Stabilization (DNS) is a complex of correction exercises with a neuromuscular approach based on improving breathing, fundamental movements, and principles of developmental kinesiology.

Whole body vibration training (WBV) is a neuromuscular training approach that has recently become very popular among researchers and practitioners in health and sport. It is usually used as an additional method in a conventional training routine.

Designing the training program to achieve the optimal benefits for PS in healthy young adults is important in general personal health management. Although different training protocols have improved PS and general stability in everyday activities, there is still considerable debate regarding the optimal exercise modalities within an exercise program.

Aim: The purpose of this study is to determine the effects of dynamic neuromuscular stabilisation (DNS), whole-body vibration (WBV), and a combination of DNS and WBV (MIX) training modalities on postural stability (PS) in healthy recreation participants.

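### The 0.80 power covers only the omnibus interaction; Holm's step-down in place of single-step Bonferroni would give the pairwise contrasts a modest power gain at the same family-wise error limit.

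*Protocol*

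**What the plan says.** All of the analysis text is in the protocol's Statistical analyses section.

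- **Sample size.** The minimum total of 140 is "given the critical $F_{(3, 136)}=2.67", with f=0.14 (partial eta squared 0.02) and "p=0.05$, $1-\beta=0.80$, groups=4, time points=2, and correlation among the measurements=0.50". Three numerator degrees of freedom with four groups and two time points identify the time-by-group interaction.
- **Order of testing.** The interaction shows whether change differs in at least one pair of groups. Within-group simple effects come next, and then: "The follow-up investigation proceeded with contrast analysis", comparing mean change between pairs of groups.
- **Multiplicity.** "The Bonferroni test corrected p-values and 95% CI; the alpha level was $p\leq0.05". The number of comparisons in the family is not given.

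The aim (Brief Summary and Study design) is to determine the effects of DNS, WBV and their combination on postural stability. The Participants section gives 58/57/57/58 randomised and a final 45/45/44/43. These final counts sum to 177, although 180 is printed as the total.

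**The concern.** A significant interaction says only that some pair of arms differs. Which modality works, and which works better, is decided by the contrasts. They are tested at a stricter level than the interaction, and the protocol gives no power for them. Two things are at stake. First, the only power figure in the plan does not describe the tests that answer the aim. Second, single-step Bonferroni leaves part of the permitted 5% unused, so some real differences between arms are missed that a step-down method with the same error limit would find.

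**Working it through.** **Inputs from the protocol:** N=140 (35 per arm if equal), partial eta squared 0.02, alpha 0.05, four groups, two time points, correlation 0.50, final arms 45/45/44/43.

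**Assumptions (not in the protocol):** a family of six pairs, since 4×3/2 = 6; and the pattern of the four mean changes, for which a range is shown. Degrees of freedom follow the plan's own 136, with none taken for the BMI covariate.

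**1. The plan's own figure.** f² = 0.02/0.98 = 0.0204, so f = 0.1429. The noncentrality is λ = f²·N·m/(1−ρ) = 0.0204×140×2/0.5 = 11.43. Critical F(3,136) = 2.671 and power = 0.808. The stated N and critical F reproduce. With f rounded to 0.14, power is 0.790.

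**2. Size of the contrasts.** On change scores λ = N·f_c², so f_c = 2×0.1429 = 0.2857. The largest standardised pairwise difference d depends on the pattern of means. Power per pair uses the noncentral t with nc = d/√(1/n₁+1/n₂) and two-sided alpha 0.05/6. At 35 per arm the critical t is 2.677.

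| Pattern of mean changes | d | nc at 35 per arm | Power, N=140 | Power, 44 v 43 | Power, 45 v 45 |
|---|---|---|---|---|---|
| Two arms v two | 2f_c = 0.571 | 2.39 | 39.0% | 50% | 52% |
| Three v one | 4f_c/√3 = 0.660 | 2.76 | 53.5% | 66% | 68% |
| Equally spaced | 6f_c/√5 = 0.767 | 3.21 | 70.1% | 82% | 83% |
| Two extremes, two midway | √8·f_c = 0.808 | 3.38 | 75.8% | 86% | 88% |

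These figures are for the largest pair only. At N=140, smaller true differences have 6-30% power under equal spacing and about 17% under the extremes pattern. If the family were only the three comparisons with CONTROL (0.05/3), the N=140 range would be 49-83%.

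**3. Gain from Holm.** Simulation with contrasts tested after a significant interaction and three training arms differing equally from CONTROL:

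| Sample | Measure | Bonferroni | Holm |
|---|---|---|---|
| N=140 | per true contrast | 53% | 56% |
| N=140 | all three found | 29% (28.6%) | 34% |
| 45/45/44/43 | per true contrast | 66% | 69% |
| 45/45/44/43 | all three found | 43% | 49% |

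Over the four patterns, Holm adds about 0.5-4 points for the largest pair at N=140.

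**4. Family-wise error per outcome** (simulated, 35 per arm, contrasts tested whether or not the interaction is significant):

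| True state | Bonferroni | Holm |
|---|---|---|
| All four equal | 0.041 | 0.041 |
| Three equal, one far away | 0.022 | 0.044 |
| Two equal pairs, far apart | 0.017 | 0.049 |

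Requiring a significant interaction first can only lower these values.

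**5. The Shaffer variant.** Once equality of four arms is rejected, at most three pairwise nulls can be true, so a step-down may start at 0.05/3. With a strict gate, the family-wise error when all arms are equal is 0.048, and per-contrast power in the pattern of step 3 is about 62% (N=140) and 74% (final sample). Without the gate, the family-wise error is 0.077.

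**The case against.** Single-step Bonferroni is a valid method, and choosing it is not an error. A reader might infer that the protocol claims 80% power for the contrasts. It does not: the figure stands beside a critical F with 3 and 136 degrees of freedom, which ties it to the interaction. That objection stands, and it limits the point to an improvement and a clarification.

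A reader might also take 39-76% as the power of the trial as run. It belongs to the planned minimum of 140. At the reported final sample the range is about 50-88%, and the largest pair passes 80% in two of the four patterns. The family of six is likewise an inference.

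The shortfall comes mainly from sizing on the omnibus test, and no step-down method brings the largest pair to 80% at N=140. That stands too.

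Holm also spends error that Bonferroni leaves unused. With one arm far from three equal ones, per-outcome error rises from 0.022 to 0.044. The protocol fits twelve models and states no correction across them. If the twelve were independent, the chance of at least one false contrast would go from 1−0.978¹² ≈ 0.23 to 1−0.956¹² ≈ 0.42. This is a fair caution. Still, Holm stays within the 5% per outcome that Bonferroni over the six pairs also guarantees, and the question of twelve outcomes arises under either method.

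Finally, the document is dated February 2024 and final testing was on 25.6.2022. A less strict adjustment adopted after results are known is post hoc, and this affects how the change may be reported.

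**Conclusion.** The point holds as a cheap improvement, not as an error in the plan. The stated 0.80 applies to the omnibus interaction only. With six pairs, single-step Bonferroni leaves the largest true contrast at about 39-76% power at N=140 and about 50-88% at 45/45/44/43, given partial eta squared 0.02, correlation 0.50 and the four assumed patterns. Holm never rejects less than Bonferroni and holds per-outcome family-wise error at or below 5% with or without a gate. It gains about 3 points per contrast and about 6 points for finding all three in the three-versus-CONTROL pattern.

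Two stronger readings are not supported. Holm does not repair the missing contrast power. Nor may the step-down simply start at 0.05/3: the section describes contrasts as following the interaction effects but does not clearly say that they are run only when the interaction is significant, and without that rule the family-wise error is about 0.08.

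**What to change.** In Statistical analyses:

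1. State the contrast family, for example all six pairs within each outcome.
2. Replace Bonferroni by Holm's step-down for the contrast p-values within each outcome, and keep the Bonferroni-adjusted 95% CIs.
3. Say beside the 0.80 that it refers to the omnibus time-by-group interaction only.
4. Use the Shaffer start at 0.05/3 only if the plan also states that contrasts are run solely after a significant interaction.
5. If results have already been seen, label the Holm p-values post hoc and show them beside the Bonferroni ones.

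The cost is a few lines of analysis outside the SPSS default: sort the six unadjusted p-values, multiply them by 6, 5, 4, 3, 2 and 1, and carry the running maximum forward. No participants, outcomes or contrasts change. The one drawback is that a Holm p-value can be significant while the Bonferroni interval for the same contrast includes zero, so the report should say that the two are adjusted differently.
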